5.1.6 Concomitant medication end date imputation

- If CM end day is missing and CM month/year are non-missing then impute CM day as the minimum of treatment end date and the last day of the month.
- If CM end day/month are missing and CM year is non-missing then impute CM day as the minimum of treatment end date and the end of the year (31DECYYYY).
- Only include if ongoing records will have an imputed CM end date. If CM day/month/year is missing then use the treatment end date + 1 day as the imputed CM end date.

If imputed CM end date is less than the CM start date, use the CM start date as the imputed CM end date.

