13. Patients who have had a pulmonary exacerbation requiring systemic glucocorticosteroid treatment and/or antibiotics in the 4 weeks prior to Visit 1. In the event of an exacerbation occurring during the screening epoch, the patient must discontinue from the study. The patient may be rescreened once the inclusion/exclusion criteria have been met.
14. Patients with active pulmonary tuberculosis.
15. Patients currently receiving treatment for nontuberculous mycobacterial (NTM) pulmonary disease.
16. Patients with one or more positive cultures in the last 12 months for *Mycobacterium avium* complex, *M. abscessus* complex, *M. kansasii*, *M. malmoense*, *M. xenopi*, *M. simiae* or *M. cheloneae*, unless all subsequent NTM cultures (at least two) are negative and in the opinion of the investigator the patient does not meet ATS criteria for NTM-pulmonary disease.
17. Hemoptysis of more than 60 mL at any time within 30 days prior to study drug administration (Visit 101).
- 18a. Estimated glomerular filtration rate (eGFR) of 50 mL/min/1.73m² or less, or an abnormal urinalysis defined as 2+ or greater proteinuria at screening (Visit 1).
19. Patients with clinically significant laboratory abnormalities (not associated with the study indication) at screening (Visit 1).
20. Patients with primary immunodeficiency receiving immunoglobulin therapy.
- 21a. Patients with primary ciliary dyskinesia (PCD) may be eligible if their hearing threshold at screening audiometry is 25dB or lower at frequencies 0.5-4 kHz.
22. Patients with active allergic bronchopulmonary aspergillosis.
23. Patients with an organ and bone marrow transplant/grant versus host disease.
24. Patients with haematological malignancies.
25. Patients with other clinically significant conditions (not associated with the study indication) at screening which might interfere with the assessment of this study.
26. Patients who are receiving inhaled anti-pseudomonal antibiotic within 28 days prior to study drug administration (Visit 101).
27. Any use of systemic anti-pseudomonal antibiotics within 28 days prior to study drug administration (Visit 101).
28. Use of loop diuretics, i.v. urea, i.v. mannitol within 7 days prior to study drug administration (Visit 101).

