Baseline data (using a specific CRF as necessary) such as spirometry, previous hospital admissions and exacerbations, baseline Medical Research Council (MRC) breathlessness score, colonization with *P. aeruginosa* and other organisms, and radiological changes will be collected for calculation of the Bronchiectasis Severity Index (BSI) for all patients. The BSI will serve as a disease-specific severity assessment tool ([Chalmers et al 2014](#)).

Previous medication to be listed includes information for all antibiotics and macrolides administered within the last 12 months prior to Visit 1.

A sputum sample is required to be collected at Visit 1, cultured locally at the site and tested for the presence of *P. aeruginosa*, to ensure patients meet the inclusion criteria.

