2.4.2 Prior, concomitant and post therapies

The latest version available prior to database lock of the World Health Organization (WHO) drug dictionary will be used to classify prior, concomitant and rescue medications by therapeutic class.

Prior medication is defined as any medication with a stop date prior to the date of the first dose of study drug.

Concomitant medication is defined as any medication with a start date prior to the date of the first dose of investigational product and continuing after the first dose of investigational product or with a start date on or after the date of the first dose of study drug.

Post-treatment medication is defined as any medication with a start date after the date of the last dose of study drug.

Rescue medication for pulmonary exacerbations (including systemic antibiotics) and for bronchospasm is allowed. Use of rescue medication will be recorded on the Concomitant medications/Significant non-drug therapies CRF.

The number and percentage of patients taking prior, concomitant and rescue medications will be summarized by treatment and by Anatomical Therapeutic Classification (ATC) and preferred term. Each prior, concomitant and rescue medication could be classified by more than 1 ATC and will be counted for each. Summary tables will be provided for rescue and concomitant medications started prior to study drug, started on or after the start of study drug and for non-cystic fibrosis bronchiectasis related medications started on or after the start of study drug. Multiple medication usage by a patient in the same category will be counted only once. Summaries will be based on the SAF.

All prior, concomitant and rescue medications and therapies will also be listed.

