2.6.3.3 Anti-pseudomonal antibiotics

Proportion of patients requiring anti-pseudomonal antibiotics

The proportion of patients requiring anti-pseudomonal antibiotics across the treatment epoch and across the entire study period will be summarized by treatment arm and by route of administration (overall, oral and parenteral).

Time to first use of anti-pseudomonal antibiotics across the entire study period

The time to first use of anti-pseudomonal antibiotics by route of administration (overall, oral and parenteral) will be analyzed using a Cox regression model stratified by baseline macrolide use. The model will include treatment as a fixed-effect factor, and number of pulmonary exacerbations in the 12 months prior to screening as a covariate. Six pairwise comparisons will be evaluated as specified in [Section 2.6.3](#). in addition two pairwise comparisons will be evaluated between pooled continuous regimens vs pooled placebo and, between pooled cyclic regimens and pooled placebo. The estimated adjusted hazard ratio for TIP over placebo will be displayed along with the associated 2-sided 95% CI.

The exposure adjusted rate of usage of anti-pseudomonal antibiotics across the entire study period

The number of anti-pseudomonal antibiotics across the entire study period will be analyzed by route of administration (overall, parenteral and oral) using a generalized linear model assuming the negative binomial distribution including treatment and baseline macrolide use as fixed-effect factors, and number of pulmonary exacerbations in the 12 months prior to screening as a covariate. The log time in study in years will be included as an offset variable in the model. Six pairwise comparisons will be evaluated as specified in [Section 2.6.3](#), in addition two pairwise comparisons will be evaluated between pooled continuous regimens vs pooled placebo and, between pooled cyclic regimens and pooled placebo. The adjusted rate of usage will be provided for each treatment arm. The estimated rate ratio together with the 2-sided 95% interval will be provided.

Duration of anti-pseudomonal antibiotic use across the entire study period

The duration of anti-pseudomonal antibiotic use (days) across the entire study period will be summarized by cohort, treatment arm and pooled cyclic and continuous regimens and by route of administration (overall, parenteral and oral).

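### SAP 5.1.6 carries a pre-study antibiotic course past first dose when its end month is unknown and its recorded end year is the year of first dose

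*SAP*

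**What the plan says.** SAP 5.1.6 has three branches for an incomplete medication end date.

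- Day missing: "impute CM day as the minimum of treatment end date and the last day of the month".
- Day and month missing: "impute CM day as the minimum of treatment end date and the end of the year (31DECYYYY".
- Whole date missing: "use the treatment end date + 1 day as the imputed CM end date". The sentence before this one is garbled but appears to confine the branch to ongoing records.

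One check follows: "If imputed CM end date is less than the CM start date, use the CM start date as the imputed CM end date". No branch refers to first dose.

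SAP 2.4.2 calls a medication prior if it stopped before first dose. It calls it concomitant if it started earlier and was "continuing after the first dose of investigational product".

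Historical antibiotics are collected by design. Protocol 6.2 states: "Previous medication to be listed includes information for all antibiotics and macrolides administered within the last 12 months prior to Visit 1". Inclusion criterion 4 requires antibiotic-treated exacerbations in the 12 months before screening. Exclusion 27 rules out "Any use of systemic anti-pseudomonal antibiotics within 28 days prior to study drug administration (Visit 101".

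Protocol 6.4.3 takes anti-pseudomonal use from the concomitant medication records. SAP 2.6.3.3 reports the proportion of users, and adds: "The duration of anti-pseudomonal antibiotic use (days) across the entire study period will be summarized by cohort". Neither section says whether a course must have started on or after first dose to count.

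**The concern.** If the recorded end year is the year of first dose, both candidates in the month-missing branch (end of treatment and 31 December) lie on or after first dose. The earlier of the two does as well. The course is then classed as concomitant, even though exclusion 27 tells us that, in an eligible patient, a systemic anti-pseudomonal course begun before the study had ended at least 28 days earlier.

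At stake are secondary summaries. One historical record with a vague end date could add a user and weeks of antibiotic days that never occurred. Every patient has recent antibiotic history, and the arms are small.

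**Working it through.** The plan gives no figure for this, so the check applies the rule as written.

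**Inputs**
- Imputed end = min(treatment end, 31 December of the recorded end year) (SAP 5.1.6).
- Last dose on Day 113 (Protocol 5.5.4), so treatment end = first dose + 112 days for a completer.
- 107 patients randomised (SAP 1); allocation 1:1:1 to cohorts and 2:2:1 within cohort (Protocol 3.1).
- Assumptions: first dose uniform over a 365-day year; true course ends uniform from 35 to 365 days before first dose.

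**Formula:** false on-study days = imputed end − first dose + 1, or zero if the imputed end precedes first dose.

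**Worked cases**

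| Course start | Recorded end | First dose | Treatment end | Imputed end | Class | False days |
|---|---|---|---|---|---|---|
| 10 Feb 2018 | month unknown, 2018 | 15 Jun 2018 | 5 Oct 2018 | 5 Oct 2018 | concomitant | 113 |
| 5 Apr 2017 | month unknown, 2017 | 10 Nov 2017 | 2 Mar 2018 | 31 Dec 2017 | concomitant | 52 |
| 5 Nov 2017 | month unknown, 2017 | 10 Feb 2018 | 2 Jun 2018 | 31 Dec 2017 | prior | 0 |

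The third case shows the boundary: an earlier end year gives a 31 December that falls before first dose.

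**All date combinations**
- Number of combinations: 365 first-dose dates × 331 end dates = 120,815.
- End year equals first-dose year: 54,615, or 45%. Each of these gets an imputed end on or after first dose; the end equals first dose only when first dose is on 31 December.
- End year earlier: none is extended.
- Among same-year courses: mean false overlap 79 days; the full 113 days in 44%.
- Sensitivity: with ends 29 to 393 days before first dose, the same-year share is 42% and the mean overlap about 80 days.

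**Effect of one record on a mean duration** (averaging over all patients in the arm, non-users as zero; the SAP does not state the denominator)
- Single active arm: 107/3 × 2/5 = 14.3 patients. 79/14.3 = 5.5 days on average; 113/14.3 = 7.9 at most.
- Pooled regimen: 107 × 2/5 = 42.8 patients. 79/42.8 = 1.8 days on average; 113/42.8 = 2.6 at most.
- For scale, as an assumption only: if 40% of patients had one 14-day course, the true mean would be 0.4 × 14 = 5.6 days.

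**Day-only branch.** The imputed month end is at most 30 days after the true end. With a true end at least 29 days before first dose, overlap is possible only at the extreme edge, so this branch is not a practical problem.

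**The case against.** Much of the case against a broader reading stands.

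- A reader might infer that every historical course with an unknown end month is extended. It is not: courses with an earlier end year, about 55% under the assumptions above, stay prior.
- A reader might add courses with no end date at all. The lead-in to that branch appears to limit it to ongoing records, so non-ongoing courses are not shown to be affected.
- A reader might average the overlap equally over all first-dose dates, which gives 96 days, with 113 days on 69% of dates. That overstates it. Same-year courses cluster among late-year first doses, where 31 December cuts the overlap short.
- Entry into the antibiotic summaries is inferred from Protocol 6.4.3 and SAP 2.4.2; it is not stated. The medication tables are split by start date and would still show the course as begun before study drug.
- A reader might infer damage to the per-protocol set. SAP 2.2 has deviations reviewed at a blinded meeting before lock, and nothing says that imputed dates decide eligibility.
- The consequence is limited. Antibiotic duration is only summarised, SAP 1 regards inference as exploratory after early closure, and pre-dose records should not favour an arm in expectation. Sites must also know roughly when recent courses ended in order to confirm eligibility, so such records may be few.

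One defence is weaker. SAP 5.1.6.1 marks date imputation for prior therapies as not applicable, but a record can be called prior only once its stop date is known or imputed.

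None of this alters the same-year result: the rule as written yields a date that the eligibility criteria contradict.

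**Conclusion.** The defect is real and narrow. It needs a non-ongoing course known to have begun before first dose, an unknown end month, and a recorded end year equal to the first-dose year. The rule then puts the end on study and 2.4.2 makes the course concomitant, which exclusion 27 shows to be false for systemic anti-pseudomonal antibiotics in an eligible patient.

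The exposure is to the proportion and duration summaries, and it depends on a point that the SAP leaves open: whether courses begun before first dose count. The sizes above rest on uniform dates and a last dose on Day 113; earlier discontinuation shortens the overlap. The documents do not give the number of affected records, so the total effect cannot be computed. The primary endpoint is not involved.

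**What to change.** Add to SAP 5.1.6: for a non-ongoing systemic anti-pseudomonal course whose recorded (not imputed) start information places it before first dose, and whose end month is missing, the imputed end is no later than the day before first dose (or the start date if later), and the course is classed as prior unless other recorded data show that it continued.

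Do not apply the cap where the pre-dose start exists only through SAP 5.1.5, that is, where the start year is missing, or is the first-dose year with the month missing or equal to the first-dose month. That rule sets such starts to the day before first dose, so a wider cap could remove courses that truly began on study.

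State in SAP 2.6.3.3 that a course known to have started before first dose, and not shown to continue past it, is not on-study use. State also that imputed dates are not used to decide breaches of exclusion 27. The capped date itself falls inside the 28-day window, while a cap placed before the window would impute compliance and could hide a real breach.

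The cost is a few sentences and one programming condition before database lock. No new data are needed, and courses shown by an ongoing flag or a complete end date to have continued are still counted.

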6.4.3 Anti-pseudomonal antibiotic use

The proportion of patients having anti-pseudomonal antibiotic and duration of treatment (other than study drug) will be determined from the collection of concomitant medications during the study.

A list of anti-pseudomonal antibiotics can be found in [Appendix 12](#).

[figure not shown]

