2.6 Analysis of secondary and exploratory efficacy objective(s)

For efficacy analysis, patients assigned to placebo arms will be pooled across the 3 cohorts, as the number of placebo capsules is not expected to impact the efficacy assessments. Unless otherwise specified, the following analysis will be conducted both over the treatment epoch (through Day 113) and over the entire study period (through Day 169).

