2.6.1.3 Anti-pseudomonal antibiotics

The following anti-pseudomonal antibiotics-related parameters will be assessed by cohort and treatment arm and also by pooled three continuous TIP regimens and pooled three cyclic TIP/placebo regimens.

[figure not shown]
- Proportion of patients requiring anti-pseudomonal antibiotics (overall, oral, parenteral)
- Time to first use of anti-pseudomonal antibiotics across the entire study period
- The exposure adjusted rate of usage of anti-pseudomonal antibiotics across the entire study period
- Duration of anti-pseudomonal antibiotic use across the entire study period

Anti-pseudomonal antibiotics will be identified prior to database lock.

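### Applied as written, the SAP's end-date rule for concomitant medications drops follow-up days of incompletely dated or ongoing antibiotics from a whole-study duration summary

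*SAP*

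**What the plan says.** **The endpoint.** SAP 2.6.1.3 lists "Duration of anti-pseudomonal antibiotic use across the entire study period" among the secondary endpoints. SAP 2.6.3.3 states "The duration of anti-pseudomonal antibiotic use (days) across the entire study period will be summarized by cohort", and also by treatment arm, pooled regimen and route of administration. SAP 2.6 ends the treatment epoch at Day 113 and the study period at Day 169. Protocol 6.4.3 gives the source: "duration of treatment (other than study drug) will be determined from the collection of concomitant medications during the study".

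**The end-date rule.** SAP 5.1.6 has four parts:

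- End day missing: "impute CM day as the minimum of treatment end date and the last day of the month".
- End day and month missing: the earlier of treatment end and 31 December of that year.
- Whole end date missing: "If CM day/month/year is missing then use the treatment end date + 1 day as the imputed CM end date".
- Floor: "If imputed CM end date is less than the CM start date, use the CM start date as the imputed CM end date".

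The sentence just before the fully-missing rule concerns ongoing records. It reads like a template instruction that was never resolved. The likely meaning is that ongoing records also get treatment end + 1 day, but the text does not settle it.

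**Which records it covers.** SAP 2.4.2 counts any drug started on or after the first dose as concomitant, with no upper time limit. It also defines a post-treatment class, started after the last dose, which overlaps with the first. SAP 5.1.6.2 marks date imputation for post therapies as not applicable.

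**How adverse events are handled.** SAP 5.1.3 caps a partial AE end date at a follow-up date, not at treatment end. SAP 5.1.4 runs an unresolved AE to study completion or discontinuation and lists it as more than x days. It leaves duration missing when a resolved AE has an incomplete end date.

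**The concern.** The endpoint's window and the rule's cap do not match. The duration is meant to cover the whole study, but an imputed end date cannot fall later than treatment end, or one day after it. The one exception is the floor, which sets the end equal to the start. For an incompletely dated or ongoing antibiotic that runs past treatment end, the days after the cap cannot be counted.

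Such records are foreseeable. Protocol 5.5.7 permits pre-planned prophylactic systemic antibiotics only during follow-up. Under Protocol 5.6.2, patients who stop study drug early remain in the study and enter a two-month follow-up, and their concomitant treatments may be collected by telephone. For these patients the cap sits at their own early stop date, so more of their time in the study lies beyond it.

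At stake is whether the summary of antibiotic days means what its label says, in a trial that stopped at 107 patients spread over nine arms.

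**Working it through.** The SAP gives no figure to reproduce here, so the check applies its rule literally to example records.

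**Inputs and assumptions**

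- Planned treatment end Day 113 and study end Day 169 (SAP 1.1 and 2.6). Follow-up is 169 - 113 = 56 days, which matches the stated length and is 56/169 = 33% of the window.
- 5.1.6 does not define treatment end date; it is taken as the last dose of study drug.
- Duration = end - start + 1, the convention of SAP 5.1.4 for AEs and 2.4.1 for exposure. No CM duration formula is given; end - start would give 0 in place of 1.
- Where a calendar month matters, the first dose is set for illustration at 1 March 2018. Day 113 is then 21 June and Day 169 is 16 August.
- Rows marked * rest on the likely reading that ongoing records go to treatment end + 1 = Day 114.

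**Results**

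| Record | True days | End under 5.1.6 | Days under 5.1.6 |
|---|---|---|---|
| Days 120-133, end day missing | 14 | min(Day 113, 31 July) = Day 113, before start, so Day 120 | 1 |
| Days 108-121, end day missing | 14 | min(Day 113, 30 June) = Day 113 | 113 - 108 + 1 = 6 |
| Ongoing Day 120 to Day 169* | 169 - 120 + 1 = 50 | Day 114, before start, so Day 120 | 1 |
| Ongoing Day 100 to Day 169* | 169 - 100 + 1 = 70 | Day 114 | 114 - 100 + 1 = 15 |
| Drug stopped Day 29, antibiotic ongoing Day 35 to Day 85* | 85 - 35 + 1 = 51 | Day 30, before start, so Day 35 | 1 |
| Days 40-53, end day missing | 14 | 30 April = Day 61 | 61 - 40 + 1 = 22 |
| Days 40-53, end month missing | 14 | min(Day 113, 31 December) = Day 113 | 113 - 40 + 1 = 74 |

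In the fifth row, follow-up runs 56 days from Day 29, to Day 85.

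The first five rows lose days; the last two gain them. For a patient who completes treatment, the largest possible loss on one record is 169 - 113 = 56 days with a partial date, or 169 - 114 = 55 days for an ongoing one.

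**Scale in a small arm.** Under the 1:1:1 and 2:2:1 allocation, an active arm expects 107 x 2/15 = about 14 patients; actual arm sizes are not given. If the mean is taken over all patients in the arm, one record cut from 50 days to 1 moves it by 49/14 = 3.5 days.

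**The case against.** The best counter-argument is that no sentence says imputed CM dates feed the duration. SAP 2.1 says data are in general reported as observed, and 2.6.3.3 gives no formula. The AE rules separate the two steps: 5.1.3 imputes an end date, while 5.1.4 leaves duration missing for a resolved event with an incomplete one. If antibiotics were handled like that, nothing would be truncated. This reading is possible, but the SAP states it nowhere for medications. Section 5.1.6 is the only CM end-date rule, and the endpoint is built from CM records.

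Second, antibiotics started after the last dose might be held to be post-treatment medications outside 5.1.6. They also meet the concomitant definition, so the rule reaches them. If it did not, they would have no rule at all, which is still a gap.

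Third, the ongoing-record examples depend on an unclear sentence. That stands. The examples with a missing end day do not depend on it.

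Fourth, the consequences are limited. Duration is only summarised, with no model or comparison. Proportion using, time to first use and rate of use do not need an end date. SAP section 1 already treats even pre-defined inference as exploratory after early closure, and Protocol 8.3 provides for data queries before lock. All of this stands, and it limits the weight of the point without making the rule fit the endpoint.

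**Conclusion.** Applied as written, SAP 5.1.6 does not suit a duration summary that runs to Day 169. Incompletely dated antibiotics, and on the likely reading ongoing ones, lose their follow-up days when they run past treatment end. Those started after treatment end count as 1 day whatever their true length. The cut falls earlier for patients who stop study drug early. The conclusion rests on imputed dates feeding the summary, treatment end meaning last dose, and end - start + 1.

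A reader might infer that the endpoint is biased downwards, and that an arm with more discontinuations would appear to need fewer antibiotic days. The documents do not support that. The same rule lengthens some courses that lie within treatment (14 days to 22 or 74 above), so the net direction is not established. No discontinuation rates by arm are given, only an overall planning figure of about 20%.

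Nor does every incomplete record end at treatment end: partial dates take the month or year end when that is earlier. The number of affected records is unknown. This is a rule worth correcting for a descriptive secondary endpoint; it does not threaten the primary analysis.

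**What to change.** For the whole-study antibiotic-duration summary only, amend SAP 5.1.6 as follows:

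- **End day missing:** cap at the earlier of month end and the patient's last-contact date, which SAP 2.1.1 already defines as end of study.
- **Ongoing:** run to last contact and flag as more than x days, as 5.1.4 does for AEs.
- **End month or whole date missing, not ongoing:** leave duration missing, in line with 5.1.4. Extending these records to last contact would make matters worse: the Days 40-53 course with end month missing would go from 74 days to 169 - 40 + 1 = 130.
- **Wording:** replace the unclear sentence on ongoing records, and state that the rule covers antibiotics started after the last dose.

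Under this rule the course ongoing from Day 120 counts 50 days, the one from Day 100 counts 70, and the Days 108-121 course counts 122 - 108 + 1 = 15. Month-end imputation remains approximate: the Days 120-133 course would count 153 - 120 + 1 = 34 days, with 31 July as Day 153. The table should therefore show how many records were imputed or ongoing in each arm.

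The cost is a short SAP edit and one programming change. No new data are needed.
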